### **7.2.4 *Electrocardiograph (ECG)***

We record the ECG results before recruitment and during the follow-up period.

### **7.2.5 *The tests of gut microbiota in feces specimens***

A net pot is delivered to each participant at the initial visit and during the follow-up period for collection of stool. Participants are required to deliver the pot with fresh stool to hospital within 4 hours, and the samples will be collected and marked by our trained study staff and frozen immediately at -80°C. The feces specimens are preserved for further test of gut microbiota in the future.

## **8. Management of Trial Drugs**

### **8.1 Registration & usage**

Patients who met the inclusion/exclusion criteria will be randomized into group A or B, and each participant will receive a number that will remain the same throughout the trial. The serial number will be recorded on the case report form (CRF). Each selected patient can only receive the corresponding medication.

The study drugs should be kept and distributed by a special person and a registration system should be established. Each patient should return the rest of drugs at the end. Patients are required to avoid taking study drugs outside the trial.

### **8.2 Dispense & storage**

To well manage and use the study drugs, each study center should establish a strict personal drug management system. At the end of the trial, the remaining drugs should be uniformly recovered and disposed. All the study drugs must be stored safely under suitable conditions.

## **9. Compliance**

To ensure a better trial completion rate, we should pay attention to the measures of subject compliance. Each participant should be fully informed of the potential benefits and risks of the study drugs and sign voluntarily the consent form. Enrollment is followed by a 2-week run-in period to identify and exclude participants who have been considered unlikely to follow the study procedures.

We should confirm that the test or control drugs are taken effectively and adequately by each participant. Follow-up is performed by telephone calls and clinical visits. A regular monthly phone call will be made by our study staffs in charge to monitor adherence and the curative and side effects of the medication until the end of the trial. A clinical visit every 3 months is planned to return any unused pills and bottle, in exchange for another 3-month dosage of drugs with the same label. Bottles of study pills were mailed to participants who had difficulties in reaching the hospital.

During the study period, if one participant is found to refuse to take the drugs (including the placebo), we should have a positive conversation with the participant and try to

persuade him/her to continue the study, and report the situation to the doctor in charge meanwhile.

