### **3.2 Randomization**

Computer-generated randomization is used to allocate participants into BBR hydrochloride group and placebo group in a 1:1 ratio. The person who generates the allocation sequence is an expert on biostatistics, who is not involved in this study. Investigators who enroll participants receive the serial numbers. Participant enrollment must be carried out according strictly to the serial numbers. Those who enroll participants and assign interventions are unaware of the details of grouping.

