#### **4.3 Elimination criteria**

1. Individuals who do not meet the inclusion/exclusion criteria.
2. Serious violation of the study protocol which has impact on the drug efficacy.
3. Presence of lost data or data unable to get.

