**Table1. Participant timeline**

|                                    | Study Period |        |                 |    |    |    |    |    |    |    |                           |
|------------------------------------|--------------|--------|-----------------|----|----|----|----|----|----|----|---------------------------|
|                                    | Allocati     | Run-in | Post-allocation |    |    |    |    |    |    |    | Closeout                  |
| Time points                        | 0            | -2wks  | M3              | M6 | M9 | 12 | 15 | 18 | 21 | 24 | M24-M36
Final visit    |
| Enrollment:                 |              |        |                 |    |    |    |    |    |    |    |                           |
| Eligibility screen                 | X            |        |                 |    |    |    |    |    |    |    |                           |
| Informed consent                   | X            |        |                 |    |    |    |    |    |    |    |                           |
| Interventions:              |              |        |                 |    |    |    |    |    |    |    |                           |
| BBR
hydrochloride or
placebo |              |        | ◆               |    |    |    |    |    |    | ◆  | Return
unused
pills |
| Assessments:                |              |        |                 |    |    |    |    |    |    |    |                           |
| Demographics                       | X            |        |                 |    |    |    |    |    |    |    |                           |
| Smoking status                     | X            |        |                 |    |    |    |    |    |    |    |                           |
| Height                             | X            |        |                 |    |    | X  |    |    |    | X  |                           |
| Weight                             | X            |        |                 |    |    | X  |    |    |    | X  |                           |
| Medical history                    | X            |        |                 |    |    |    |    |    |    |    |                           |
| Family history                     | X            |        |                 |    |    |    |    |    |    |    |                           |
| Manifestations                     | X            |        | ◆               |    |    |    |    |    |    | ◆  |                           |

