| Laboratory tests                   | X            |        |                 |    |    | X  |    |    |    | X  |                           |
| Colonoscopy                        | X            |        |                 |    |    | X  |    |    |    | X  |                           |
| Histology                          | X            |        |                 |    |    | X  |    |    |    | X  |                           |
| Stool samples                      | X            |        |                 |    |    | X  |    |    |    | X  |                           |
| Drug distribution                  |              | ◆      |                 |    |    |    |    |    |    | ◆  |                           |
| Adverse event                      | X            |        | ◆               |    |    |    |    |    |    | ◆  |                           |
| Medication                         |              | ◆      |                 |    |    |    |    |    |    | ◆  |                           |

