## 13.2 Statistical analysis

### 13.2.1 Balance analysis

Full Analysis Set (FAS) is used in the balance analysis. This analysis set includes all the subjects to the principle of intention to treat (ITT). The subjects must have received at least one follow-up colonoscopy.

A balance analysis is performed for baseline data to evaluate the comparability of the two groups. The baseline data include the number of patients enrolled, the number of clinically evaluable patients, age, weight, symptoms, signs and laboratory tests. In the balance analysis, quantitative variables are described using the mean, standard deviation (SD), normal distribution W test and  $P$  value, etc. The t test or the Wilcoxon rank sum test (if abnormal distribution) is used for comparison the difference between the test drug group and the control group in the statistical analysis. Categorical variables are described using cases and percentages. The chi-square ( $\chi^2$ ) test, the Mantel-Haenszel  $\chi^2$  test or the Fisher's exact test is used for analyzing categorical data.

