### 13.2.2 Efficacy analysis

The trial results are evaluated by FAS and Per Protocol Set (PPS). FAS is mainly used to compare the treatment effect for the primary endpoint, and regarding the statistical results from PPS as supplementary analysis. If the subjects have not completed all the treatment, the last exam result will be treated as last observation carried forward (LOCF). Risk ratios (RR) and 95% confidence intervals (CI) are used as the efficacy indicator, comparing by Mantel-Haenszel  $\chi^2$  test methods between the two groups.

Unconditional logistic regression is conducted to compute the odds ratio to estimate the relation between BBR intervention and recurrence of A-CRA and non A-CRA (NA-CRA). Kaplan-Meier method is conducted to estimate progression-free survival of no recurrence of adenoma with log-rank test to compare the survival curve between BBR and placebo group. Survival Curve is used to illustrate time to recurrence of adenoma and RRs are illustrated by Forest plots. We perform predefined subgroup analyses of the primary outcomes to assess BBR effect in terms of age, gender, smoking status, BMI, family history of CRC, number of adenoma and history of CRA.

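### The plan contradicts itself on whether the excluding 2-week run-in comes before or after randomisation; if after, randomised participants can leave the primary comparison

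*Combined protocol and SAP*

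**What the plan says.** **Order of events.** Section 9 says "Enrollment is followed by a 2-week run-in period to identify and exclude participants who have been considered unlikely to follow the study procedures". Section 3.2 links enrolment to the pre-generated allocation list: "Participant enrollment must be carried out according strictly to the serial numbers". Section 8.1 gives the trigger for randomisation: "Patients who met the inclusion/exclusion criteria will be randomized into group A or B". The criteria in sections 4.1 and 4.2 contain nothing about completing a run-in.

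**Table 1.** The first column is allocation, with the eligibility screen and informed consent marked in it. The next headings are "Run-in | Post-allocation". The time labels beneath are 0 for allocation and minus two weeks for the run-in. The "Drug distribution" row and the medication row are first marked in the run-in column. The study-treatment row in the Interventions block is blank there and first marked at month 3.

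**Analysis.** Section 13.2.1 describes the Full Analysis Set (FAS) as following intention to treat, then adds: "The subjects must have received at least one follow-up colonoscopy". Section 13.2.2 says "FAS is mainly used to compare the treatment effect for the primary endpoint". Section 4.3 lists among its elimination criteria: "Presence of lost data or data unable to get". No section says how people excluded during the run-in are counted, followed or analysed.

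**The concern.** A run-in that screens out likely non-adherers is an accepted enrichment device if it is finished before allocation. It then narrows the population but leaves the randomised comparison intact. After allocation, the same exclusions remove people from groups formed by randomisation, and intention to treat no longer describes what is analysed.

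The documents do not settle which of these the trial does, and sites could legitimately differ. If assigned pills were taken in the run-in, early tolerability could make exclusions differ by arm even under blinding; section 6.4 anticipates severe constipation after study pills. Such exclusions could also go unseen if participants are counted only from the end of the run-in.

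**Working it through.** **1. The order, source by source**

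| Source | What it implies |
|---|---|
| Section 9 | Run-in after enrolment; its purpose is exclusion |
| Section 3.2 | Enrolment proceeds by allocation serial number |
| Section 8.1 with 4.1 and 4.2 | Randomisation on eligibility; no run-in condition |
| Table 1, column order | Allocation, run-in, post-allocation |
| Table 1, time labels | Run-in at minus two weeks, allocation at 0: run-in first |

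The first four point to a run-in after assignment, though none says so outright. The time labels point the other way. Read literally, the labels also put the run-in before consent and eligibility, because both are marked at time 0. Neither reading leaves Table 1 and section 9 consistent.

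**2. What is taken in the run-in.** The drug-distribution and medication rows suggest pills are in use during it. The study-treatment row suggests assigned treatment starts afterwards. The documents do not resolve this.

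**3. Route out of the primary analysis, if the text order is followed.** The first scheduled follow-up colonoscopy in Table 1 is at month 12. Someone excluded at week 2 has none unless deliberately followed, so fails the FAS condition in section 13.2.1 and is absent from the main comparison in section 13.2.2. This follows from the FAS rule; it is not a stated rule for run-in failures.

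**4. Possible bias.** Input from section 13.1: placebo recurrence 30%. Assumptions, since the documents give no rates: no drug effect, 45% recurrence among those excluded in both arms, and a fraction *a* of each arm excluded.

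Retained risk = (0.30 − *a* × 0.45) / (1 − *a*)

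- *a* = 2%: 0.291 / 0.98 = 0.2969
- *a* = 3%: 0.2865 / 0.97 = 0.2954
- *a* = 5%: 0.2775 / 0.95 = 0.2921
- *a* = 10%: 0.255 / 0.90 = 0.2833

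| Excluded, BBR vs placebo | Number of 500 per arm | Apparent risk ratio |
|---|---|---|
| 2% vs 2% | 10 vs 10 | 0.2969 / 0.2969 = 1.00 |
| 5% vs 2% | 25 vs 10 | 0.2921 / 0.2969 = 0.98 |
| 10% vs 3% | 50 vs 15 | 0.2833 / 0.2954 = 0.96 |

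If those excluded have the same 30% risk as everyone else, the ratio stays at 1.00 and only participants are lost. The planned ratio is 0.21 / 0.30 = 0.70.

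**5. Sample size.** The plan's 918 reproduces. For 30% vs 21%, two-sided 0.05, 80% power and pooled variance:

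n = [1.960 × √(2 × 0.255 × 0.745) + 0.842 × √(0.30 × 0.70 + 0.21 × 0.79)]² / 0.09² = 367 per arm

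367 / 0.8 = 459 per arm after rounding up, or 918 in total. No separate allowance for run-in exclusions is named. With a run-in loss added to the 20% dropout:

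| Run-in loss | Power from 918 | Power from 1000 |
|---|---|---|
| 0% | 80.0% | 83.3% |
| 2% | 79.2% | 82.5% |
| 5% | 78.0% | 81.4% |
| 10% | 75.7% | 79.2% |

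At the 1000 planned in section 5, power is therefore a secondary matter.

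**The case against.** The strongest reply is that the trial may well run the run-in first. The Enrollment block of Table 1 lists only the eligibility screen and consent, so enrolment in section 9 can be read as consent. Consent, run-in, allocation then fits section 9 and the order of the two time labels. Section 3.2 does not say the serial number is issued before the run-in. The allocation heading is cut short in the available text, so column layout alone is weak evidence. All of this stands: a reader might infer that the run-in definitely follows allocation, and the documents do not establish it. What survives is that no section makes randomisation wait for the run-in, and section 8.1 and the column order suggest that it does not.

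A reader might also infer that the run-in is spent on assigned pills, so that BBR-intolerant participants are filtered out. The study-treatment row, first marked at month 3, stands against that. Section 6.4 speaks of either group and gives no rate by arm, and severe constipation at baseline is already an exclusion criterion in section 4.2.

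Finally, one could assume the 45% risk for excluded BBR participants only. Placebo then stays at 0.30 and the ratios become 0.2969 / 0.30 = 0.99, 0.2921 / 0.30 = 0.97 and 0.2833 / 0.30 = 0.94. This produces a shift even when 2% are excluded from each arm, so it builds the asymmetry into the assumption. Nothing in the documents supports treating the arms differently.

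**Conclusion.** The concern holds conditionally. The documents contradict themselves on whether the run-in precedes or follows randomisation, and on what is taken during it. If the order in the text is followed, exclusions happen after randomisation and the colonoscopy condition carries them out of the FAS. That exclusion after randomisation has occurred, or that it differs by arm, is not shown.

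The illustrative bias is small: a risk ratio of 0.96 to 1.00 under no effect, against a planned 0.70. It rests on assumed exclusion rates of 2–10% on BBR and 2–3% on placebo, and an assumed 45% risk in those excluded from either arm. The point still deserves correction rather than a clarifying note, because it decides who belongs to the randomised population.

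**What to change.** **Order.** Reconcile sections 3.2, 8.1 and 9 and Table 1 so that consent, eligibility and the run-in all come before randomisation. Issue the serial number and allocated pills only once the run-in is completed. Reorder Table 1 as run-in (minus two weeks), allocation (0), post-allocation, with consent and eligibility marked no later than the start of the run-in. Make the drug-distribution, medication and study-treatment rows agree, and state that what happens in the run-in is the same for everyone.

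**Anyone already randomised before the run-in.** Do not remove them from the randomised population on run-in grounds. Report their number by arm, keep them in the Safety Set if dosed, and include any follow-up colonoscopy already scheduled or obtainable.

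**Cost.** Rewording, and a serial number issued two weeks later. Somewhat more people must be consented to reach 1000 randomised: at assumed run-in losses of 2%, 5% or 10%, 1000 / 0.98 = 1021, 1000 / 0.95 = 1053 or 1000 / 0.90 = 1112. Run-in failures already allocated re-enter the denominator and may dilute the effect. If such failures made up 2%, 5% or 10% of the BBR arm and had the 30% placebo rate (an assumption separate from the 45% above), the BBR rate would be 0.21 × (1 − *a*) + 0.30 × *a* = 21.2%, 21.5% or 21.9%. Power with 400 evaluable per arm would be 81.7%, 79.1% or 74.4%. That is the price of keeping the comparison as randomised, and it applies only to people already allocated this way.

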## **10. Discontinuation of Trial**

1. The case found to be inconsistent with the inclusion criteria after recruitment.
2. It is difficult to adhere to the treatment for the patient who is in a worse condition after medication. In that case, the investigator can suspend the trial and treat as an invalid case.
3. Serious or intolerable adverse events.
4. Serious violation of the study protocol during the study period.
5. Poor compliance.
6. Lost in contact for various reasons.
7. Withdrawal of the consent form by the participant.
8. Discontinuation of trial asked by the sponsor.
9. Discontinuation of trial suggested by the investigators.

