### **7.2.3 *Colonoscopic examination***

Participants at each center are informed to undergo at least one or two follow-up colonoscopies until the last enrolled patient reached the 2-years follow-up, by a training endoscopist to investigate whether new adenoma will be taken place, using a standard colonoscope.

Bowel preparation includes 1000ml polyethylene glycol electrolyte solution administered the previous evening and 2000ml in the early morning before an intraday examination. If the colonoscopy does not reach the caecum, it cannot be included for further analysis and the patient will be required to undergo colonoscopy by another skilled endoscopist on next occasion. The mean colonoscopy withdrawal time are required to be 6 minutes or more.

According to a multiple-center study based of Chinese population [12], the peak of recurrence of adenomas is almost entirely concentrated in the first year, and the first three years follow-up after polypectomy is of critical importance in China. The similar opinions are recommended in *2011 Consensus on the Prevention of Colorectal Tumors in China* [13].

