## **11. Endpoints**

The primary endpoint is the recurrence of CRA at any follow-up colonoscopy in both groups during the whole trial. The number, size and location of all adenomas are assessed.

The secondary outcomes are the incidence rates of all polypoid lesions (hyperplastic polyps, inflammatory polyps, serrated polyps, etc.), as well as advanced adenoma or CRC at any follow-up colonoscopy in both groups.

All retrieved polypoid lesions should be sent to local pathology laboratory for histologic evaluation. Two experienced pathologists at each center, who are unaware of the treatment assignments, must review the slides for all removed colorectal lesions. Disagreements in the histologic diagnosis are resolved by re-examination by these two pathologists until agreement is reached. We classify the location of a lesion as right

sided (caecum, ascending colon, hepatic flexure, and transverse colon) or left sided (splenic flexure, descending colon, sigmoid colon, and rectum), and define advanced CRA (A-CRA) as an adenoma with a diameter of 10 mm or more, a villous adenoma ( $\geq 25\%$  villous) or an adenoma with high-grade dysplasia.

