## **17. Follow-up & Medical Measures After the Trial**

If adverse events persist after discontinuation of the study drugs, the patients should be followed and receive reasonable treatment until clinical recovery or their conditions have been stabilized with corresponding records on the CRFs. If the participant suffers from health damage due to adverse drug reactions, he/she will receive appropriate medical compensation given by sponsor.

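### Section 10 lets drug-related events end trial participation and no section keeps colonoscopy follow-up going, so primary outcomes can be lost or cut short

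*Combined protocol and SAP*

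**What the plan says.** Section 10 is one list of nine items under the heading Discontinuation of Trial. Item 3 is "Serious or intolerable adverse events" and item 5 is "Poor compliance". Serious protocol violation is item 4. Lost contact (item 6) and withdrawal of consent (item 7) stand in the same list with the same status. For a patient who worsens on medication, item 2 adds: "In that case, the investigator can suspend the trial and treat as an invalid case".

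Five other places bear on what happens next:

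- Section 11 defines the outcome: "The primary endpoint is the recurrence of CRA at any follow-up colonoscopy in both groups during the whole trial".
- Section 7.2.3 asks for "at least one or two follow-up colonoscopies until the last enrolled patient reached the 2-years follow-up". Table 1 schedules these at months 12 and 24. Neither place mentions participants who are off drug.
- Section 13.2.1 restricts the full analysis set (FAS): "The subjects must have received at least one follow-up colonoscopy".
- Section 13.2.2 says: "If the subjects have not completed all the treatment, the last exam result will be treated as last observation carried forward (LOCF").
- Section 17 recognises stopping the drug as an event of its own, but only for safety: "If adverse events persist after discontinuation of the study drugs, the patients should be followed and receive reasonable treatment until clinical recovery".

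Section 9 points the other way. Staff are to try to persuade a participant who refuses the pills to stay in the study, and monthly calls run to the end of the trial.

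**The concern.** Stopping the study drug and leaving follow-up are different events, and section 10 does not separate them. A participant who cannot tolerate the pills but still consents to colonoscopy can be handled like one who has withdrawn consent. Whether the primary outcome is observed may then depend on tolerability and adherence, which can differ between berberine and placebo. The protocol itself makes a difference plausible: section 6.4 foresees severe constipation after taking study pills, section 4.2 excludes people who already have it, and section 1 describes berberine as a long-used treatment for diarrhea. The documents do not say how large the difference might be.

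At stake is the randomised comparison on the primary endpoint. No analysis can recover an examination that was never done.

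**Working it through.** **1. What happens to a participant who exits under item 3 or item 5.**

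- *Exit before month 12.* Table 1 schedules no follow-up colonoscopy before then. If none is done afterwards, there is no result to carry forward and the FAS condition in section 13.2.1 is not met. The outcome is absent.
- *Exit after a clear month-12 examination.* The participant is in the FAS as free of recurrence. An adenoma that a month-24 examination would have found is not counted, although section 11 counts any follow-up examination. The outcome is truncated.
- *Exit after an examination that found an adenoma.* The binary endpoint is already settled and is not affected.

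**2. The plan's own figure.** Inputs from section 13.1: 30% against 21% recurrence, 80% power, significance level 0.05, 20% dropout. Section 13.2.4 makes the test two-sided. With the pooled formula and mean rate 0.255:

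n = [1.960·√(2·0.255·0.745) + 0.842·√(0.30·0.70 + 0.21·0.79)]² / 0.09² = 367 per arm, or 734 in total.

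734 / 0.80 = 917.5, rounded up to 918, as the plan states. The allowance amounts to 0.20 × 918 ≈ 184 people, or 200 of the 1000 planned in section 5. It restores the number of participants and so protects power. It does nothing about who is missing. It also covers every cause of loss, including lost contact and withdrawn consent.

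**3. Illustration of bias.** All inputs here are assumptions except the 30% placebo rate. There is no drug effect, true recurrence is 30% in both arms, and 25% of berberine and 15% of placebo participants leave before any examination. If leavers have true risk r and a fraction d leaves, the rate among those examined is (0.30 − d·r)/(1 − d).

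| Leavers' risk r | Berberine (d = 0.25) | Placebo (d = 0.15) | Observed RR |
|---|---|---|---|
| 20% | 0.250/0.75 = 33.3% | 0.270/0.85 = 31.8% | 1.05 |
| 30% | 0.225/0.75 = 30.0% | 0.255/0.85 = 30.0% | 1.00 |
| 40% | 0.200/0.75 = 26.7% | 0.240/0.85 = 28.2% | 0.94 |
| 50% | 0.175/0.75 = 23.3% | 0.225/0.85 = 26.5% | 0.88 |

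Starting from 500 per arm (375 and 425 examined), a pooled two-sided test at 5% rejects in 7.8% of trials at r = 40% and in 17.5% at r = 50%. With equal loss of 20% in each arm the RR is 1.00 whatever r is. Both conditions are therefore needed: exit that depends on arm, and a different risk in leavers.

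**4. What continued follow-up does to power.** Assume complete follow-up of 500 per arm, placebo risk 30%, and berberine stoppers who revert to 30%. The berberine rate is 0.21(1 − s) + 0.30s for stopping fraction s.

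- s = 0: 21.0%, power 90.5%
- s = 5%: 21.45%, power 87.2%
- s = 10%: 21.9%, power 83.3%
- s = 20%: 22.8%, power 73.4%

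The stopping fractions and the full reversion to 30% are assumed.

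**The case against.** A reader might infer that section 10 orders colonoscopy to cease, so that the primary outcome is missing in everyone who stops the drug. The documents do not support that. Section 10 is a bare list and cancels no examination. Section 7.2.3 addresses participants at each center with no on-drug condition, section 11 counts any follow-up examination, and section 9 wants drug refusers kept in the study. Section 13.2.1 invokes intention to treat. Section 13.2.2 keeps people with incomplete treatment in the analysis, and the last examination it carries forward could be one done off drug. All of this stands, so non-collection is an inference.

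The inference is still a natural one. The heading ends the trial, not the drug. Section 9 gives no instruction if persuasion fails, and no section orders an examination after an exit under section 10. The intention-to-treat wording governs who is analysed, not whether an examination takes place.

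Two further limits stand. Anyone leaving after month 12 has a result, and section 7.2.3 itself places most recurrence in the first year, so truncation may matter less than early exit. The same paragraph, however, treats the first three years as critical. And the 20% dropout cannot be read as the size of this problem, since much of it may be loss that no wording would prevent.

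**Conclusion.** The point holds as a gap in the rules for outcome collection. As written, section 10 lets a site end follow-up for treatment-related reasons. The consequence is an absent primary outcome for exits before month 12 and a truncated one for exits after a clear examination. This conflicts with the whole-trial endpoint in section 11 and with the aim of section 9.

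The size of any bias cannot be fixed from the documents, and neither can its direction. The range of RR 0.88 to 1.05 under no true effect rests on an assumed 25% against 15% early exit and an assumed leaver risk of 20% to 50%. If exit is unrelated to arm, or leavers have the same risk as others, there is no bias from early exit. It would be wrong to conclude that the trial is biased in favour of berberine. The gap deserves correction because the loss would be irreversible and the examinations are already scheduled.

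**What to change.** Amend section 10 to state three things:

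1. Follow-up ends only on withdrawal of consent for follow-up, lost contact, or closure of the trial by the sponsor.
2. In every other listed case the participant, whether or not study drug is stopped, keeps the Table 1 colonoscopies and the telephone contact. If drug is stopped, the date and reason are recorded.
3. These examinations count for the primary endpoint in the FAS.

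Reconcile section 10, including the wording of item 2, with the retention aim of section 9 and with section 17, which now provides only for adverse events that persist after drug is stopped. The change takes no position on when drug should be stopped.

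The cost is protocol wording and one case report form page; no colonoscopy is added to the schedule. Counting off-drug examinations may dilute the estimated effect, and the loss of power is not always slight: under the assumptions above, about 83% if 10% stop and 73% if 20% stop, the latter below the planned 80%. Nor can the change recover examinations for participants already closed out, which matters because version 1.0 dates from July 2014 and the final version from December 2018.
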